2.5 Interim analyses

No interim analyses are planned for this study.

2.6 Other topics

No other topics will be studied.

2.7 Determination of sample size

A total sample size of 1000 randomized patients per treatment arm (in 1:1 allocation ratio to vildagliptin + metformin and metformin monotherapy) is planned.

The sample size calculation assumed that all randomized patients are to be followed up for 5 years unless patients dropped out from the study for various reasons (lack of efficacy, AEs, abnormal labs, lost to follow-up etc.), and that the yearly dropout rate is 11% (estimate based on ADOPT data (Kahn S et al, 2006)).

The existing vildagliptin study data suggest that approximately 10% of vildagliptin patients will have an HbA1c >7.0% after the first 3 months of the study (initial response phase), since those patients who are randomized with an HbA1c measurement above the failure threshold (7.0%) may never have an HbA1c measurement below the required threshold during the study and will therefore be counted as failures during the first 13 weeks. A similar proportion is assumed for the comparator arm. Hence it is expected that the difference in failure rate is likely to be small early in the study, but will diverge as the study progresses. The power calculations have been adjusted to take this assumption into account using statistical simulations.

The simulations showed that assuming an annual initial treatment failure rate of 7.1% in the metformin monotherapy arm (estimated based on ADOPT data), incorporating a 10% initial failure rate after 13 weeks in each treatment arm (due to some patients with baseline HbA1c $\geq 7.0\%$), 1000 patients per treatment arm would be sufficient to detect a hazard-ratio of 0.75 between vildagliptin + metformin and metformin alone (corresponding to a risk reduction rate of 25% in vildagliptin + metformin group versus metformin alone) with approximate 75% power and a 1-sided significance level of 0.025 (corresponding to a 2-sided test at 0.05).

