9.6 Sample size calculation

A total sample size of 1000 randomised patients per treatment arm (in 1:1 allocation ratio to vildagliptin + metformin and metformin monotherapy) is planned.

Power calculation for the time-to-treatment failure variable

The sample size calculation assumes that all randomised patients are to be followed up for 5 years unless patients dropped out from the study for various reasons (lack of efficacy, AEs,

abnormal labs, lost to follow-up etc.), and that the yearly dropout rate is 11% (estimate based on ADOPT data (Kahn S et al, 2006)).

The existing vildagliptin study data suggest that approximately 10% of vildagliptin patients will have an HbA1c >7.0% after the first 3 months of the study (initial response phase), since those patients who are randomised with an HbA1c measurement above the failure threshold (7.0%) may never have an HbA1c measurement below the required threshold during the study and will therefore be counted as failures during the first 13 weeks. A similar proportion is assumed for the comparator arm. Hence it is expected that the difference in failure rate is likely to be small early in the study, but will diverge as the study progresses. The power calculations have been adjusted to take this assumption into account using statistical simulations.

The simulations showed that assuming an annual initial treatment failure rate of 7.1% in the metformin monotherapy arm (estimated based on ADOPT data), incorporating a 10% initial failure rate after 13 weeks in each treatment arm (due to some patients with BL HbA1c $\geq 7.0\%$), 1000 patients per treatment arm would be sufficient to detect a hazard-ratio of 0.75 between vildagliptin + metformin and metformin alone (corresponding to a risk reduction rate of 25% in vildagliptin + metformin group *versus* metformin alone) with approximate 66% power and a 1-sided significance level of 0.025 (corresponding to a 2-sided test at 0.05).

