2.2.2.3 Statistical model, hypothesis, and method of analysis

Time to initial treatment failure

The primary statistical hypothesis of time to initial treatment failure will be assessed by a 1-sided test of superiority of the combination treatment with vildagliptin + metformin versus metformin monotherapy with α -level of 0.025 with a null hypothesis that the hazard-ratio between the combination treatment vildagliptin + metformin and metformin monotherapy is equal or greater than 1, versus the 1-sided alternative hypothesis that the hazard-ratio is less than 1:

$H_0: \lambda_{\text{vildagliptin+metformin}}/\lambda_{\text{metformin}} \geq 1$

versus

$H_a: \lambda_{\text{vildagliptin+metformin}}/\lambda_{\text{metformin}} < 1$

where $\lambda_{\text{vildagliptin+metformin}}$ and $\lambda_{\text{metformin}}$ are the hazard-rates of the initial treatment failure for vildagliptin 50mg bid + metformin up to 1000mg bid and metformin up to 1000mg bid monotherapy respectively.

The time to confirmed failure will be derived as the time from randomization to the second of two consecutive scheduled visits (after remapping in [section 1.3.3](#) has been applied), at which HbA1c $\geq 7.0\%$ is measured, starting from Visit 4 (13 weeks after randomization).

The primary efficacy analysis will use a Cox proportional hazard regression model to assess the probability of initial treatment failure, with treatment approach and geographic region as classification variables and baseline HbA1c as a covariate. The hazard-ratio and associated 95% confidence interval as well as the p-value estimated from the above model will be presented by treatment approach.

The initial treatment failure rate over time by treatment approach will be summarized using estimates and 95% confidence intervals from a Kaplan-Meier analysis. The Kaplan-Meier estimates will be plotted, with symbols to indicate censored values.

The primary analysis for this primary efficacy variable will be performed using the FAS. It will be performed in the PPS as supportive analysis as well.

The model assumptions will be checked by plotting the Schoenfeld residuals for the treatment effect obtained from the model against time. A random spread of residuals with no clear pattern will indicate that the proportional hazards assumption is valid. The results will be presented in CSR Section 16 table(s).

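### The HR of 0.75 that the trial is sized for is the effect after the initial phase; the primary Cox model would be expected to return about 0.82 to 0.83

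*SAP*

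**What the plan says.** Protocol 9.6 and SAP 2.7 (V3.0 and Addendum 1) describe one target. The SAP calls the sample "sufficient to detect a hazard-ratio of 0.75 between vildagliptin + metformin and metformin alone (corresponding to a risk reduction rate of 25" per cent; the protocol has the same clause, "sufficient to detect a hazard-ratio of 0.75 between vildagliptin + metformin and metformin alone", and the same 25%.

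The paragraph just before explains that about 10% of patients in each arm are expected to fail in the first 13 weeks because they start above the threshold. It concludes: "Hence it is expected that the difference in failure rate is likely to be small early in the study", with divergence later. It adds that the power was adjusted for this by simulation. Neither document says that 0.75 applies only to the later failures, or what overall HR the simulations produced.

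The stated powers differ by text:
- Protocol 9.6, 11% yearly dropout: "66% power and a 1-sided significance level of 0.025".
- SAP V3.0 section 2.7, about 4% yearly dropout: "with approximate 75% power".
- SAP Addendum 1 section 2.7, 11% yearly dropout: also 75%.

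The primary analysis (Protocol 9.4.2, SAP 2.2.2.3) is one Cox model timed from randomization, counting failures from Visit 4 on, with one treatment term. The SAP checks proportionality by a Schoenfeld residual plot: "A random spread of residuals with no clear pattern will indicate that the proportional hazards assumption is valid". It gives no step to follow if a pattern appears.

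**The concern.** The early failures are events in the primary analysis. If they occur equally in both arms, a single Cox HR averages an early HR of 1 with the later HR, and cannot equal the later HR. A target of 0.75 between the arms and a 10% block of early failures with no treatment effect therefore cannot both describe the overall HR.

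The sample-size section sets the effect against which the result will be read. If every planning assumption held, the trial would be expected to report an HR near 0.82 or 0.83, and a reader would wrongly judge that to fall short of 0.75. The plan also expects non-proportional hazards by its own account, yet plans no HR for the later phase.

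**Working it through.** **Inputs from the documents.** SAP 2.7: "A total sample size of 1000 randomized patients per treatment arm (in 1:1 allocation ratio to vildagliptin + metformin and metformin monotherapy) is planned"; "1-sided significance level of 0.025 (corresponding to a 2-sided test at 0.05"; control failure rate 7.1% per year; 10% early failures in each arm; 5 years of follow-up. Dropout is 11% per year (Protocol 9.6, Addendum 1) or 4% (SAP V3.0).

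Yearly hazards:
- Control: −ln(1 − 0.071) = 0.0736.
- Combination, late phase: 0.75 × 0.0736 = 0.0552.
- Dropout: −ln(0.89) = 0.1165, or −ln(0.96) = 0.0408.

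**Assumptions, not in the documents.** Event and dropout times are exponential, early failures fall at Week 13 with HR 1, and the late hazard runs from Week 0 or from Week 13. These were varied.

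**Step 1: reproduce the stated powers.** Each row is 3,000 simulated trials with exactly 10% early failures per arm and a Cox model with treatment only.

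| Dropout | Late hazard from | Events | Mean Cox HR | Power | Stated |
|---|---|---|---|---|---|
| 11% | Week 0 | 575 | 0.824 | 66.1% | 66% (Protocol 9.6) |
| 11% | Week 13 | 553 | 0.829 | 61.4% | |
| 4% | Week 0 | 648 | 0.818 | 76.0% | 75% (SAP V3.0) |
| 4% | Week 13 | 626 | 0.822 | 72.6% | |

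Six further variants per dropout rate (for example random rather than fixed early failures, or early failures exempt from dropout) gave power of 62 to 65% at 11% and 71 to 76% at 4%, with HR 0.825 to 0.829 and 0.818 to 0.821.

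**Step 2: closed-form check of the HR.** This uses the late hazard from Week 13 and weights the log HR by events.
- 11% dropout: 194 early + 358 late = 552 events; exp[(358/552) × ln 0.75] = 0.830.
- 4% dropout: 198 early + 428 late = 626 events; exp[(428/626) × ln 0.75] = 0.821.

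**Step 3: what an overall HR of 0.75 would give.** Schoenfeld power is Φ(½√D × |ln HR| − 1.96), with D events.
- D = 552: Φ(11.75 × 0.2877 − 1.96) = Φ(1.42) = 92%.
- D = 626: Φ(12.51 × 0.2877 − 1.96) = Φ(1.64) = 95%.
- D = 648: Φ(12.73 × 0.2877 − 1.96) = Φ(1.70) = 96%.

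Letting the late HR fall until the blend is 0.75 needs a late HR of about 0.64 to 0.655. That leaves 532 and 605 events and still gives 91% and 94%. In reverse, 66% power with 552 events implies an HR of 0.817, and 75% with 626 events implies 0.81. None of this fits 0.75 as the overall HR.

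**Step 4: covariates.** The primary model also adjusts for baseline HbA1c and, in the SAP, region. A rough check with HbA1c (assumed SD 0.4, 60 trials per setting, no region) gave adjusted HRs of 0.82 to 0.85. The exact value depends on how baseline HbA1c relates to failure, which the documents do not give.

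**Step 5: the Addendum pairing.** Across all variants run at 11% dropout, power was 57 to 66%, so the 75% in Addendum 1 does not reproduce. The 75% belongs with the 4% dropout of V3.0.

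**The case against.** The strongest reply is that nothing was hidden. The sample-size text names the equal early failures, predicts a small early difference, says the power was simulated accordingly, and lists the 7.1% and the 10% separately, so 0.75 can be read as an input applied to the annual rate. This stands in part. It shows that the powers in Protocol 9.6 and SAP V3.0 already contain the dilution. It does not rescue the sentence itself, which offers 0.75 and 25% as the effect between the arms and never gives the overall HR.

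A reader might infer more than the documents support:

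- **That the trial is underpowered or the sample size wrong.** The 66% and 75% reproduce with the dilution included.
- **That later durability has no planned estimate.** Protocol 9.5.2.2 and SAP 2.2.3.3 plan a between-arm comparison of the HbA1c slope from Week 26 to the end of Period 1, and Kaplan-Meier failure rates by arm are planned with 95% confidence intervals. What is missing is only a later-phase HR.
- **That the true reduction is 16%, against 25%.** Five-year failure under the inputs is 1 − 0.9 × exp(−0.0736 × 5) = 37.7% against 1 − 0.9 × exp(−0.0552 × 5) = 31.7%, a 16% relative reduction. But the plan's 25% is 1 − HR. Even a fully proportional HR of 0.75 without early failures gives 30.8% against 24.1%, about 22%. The like-for-like contrast is 25% against 17 to 18%.
- **That 0.83 is the expected adjusted result.** The covariate effect is unknown (Step 4).

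**Conclusion.** The point holds as a mislabelled target effect that should be corrected. Under the plan's own inputs, 0.75 is the HR after the initial phase. The single Cox HR is expected to be about 0.82 at 4% dropout and 0.82 to 0.83 at 11%, unadjusted. With non-proportional hazards that average shifts slightly with dropout.

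This rests on exponential times and on early failures being equal in the two arms. The timing conventions are not stated, but none of those tried brought the HR near 0.75. The sponsor's simulation output would settle the exact figure. The expected non-proportionality, with only a residual plot and no later-phase HR, is a secondary gap.

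**What to change.** 1. In Protocol 9.6 and SAP 2.7, state that 0.75 is the HR after the initial phase and that the overall Cox HR implied by the same simulations is about 0.82 to 0.83 before covariate adjustment, to be confirmed from the sponsor's simulations. Drop 25% as the overall reduction.
2. Optionally, add to SAP 2.2.2.3 a supportive piecewise Cox model. The cut should fall after the Visit 5 window closes, at about Week 30 (26 weeks plus the 28 days of SAP 1.3.2). An event needs two consecutive visits from Visit 4, so Visit 5 is the first possible event visit and a cut at Week 26 would split the early failures. With those spread evenly over 7 or 28 days either side (an assumption; 400 trials per setting), the HR after Week 26 came out at 0.79 to 0.80. It was 0.75 only with the later cut. The later HR compares patients still free of failure, so it is supportive only. If added after unblinding, it should be labelled post hoc, as Addendum 1 does for its other additions.
3. Reconcile the 11% dropout and 75% power in SAP Addendum 1 section 2.7 with Protocol 9.6 and SAP V3.0.

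The primary test and sample size stay unchanged. The cost is a few sentences, one corrected pairing and, if wanted, one extra model.

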2.7 Determination of sample size

A total sample size of 1000 randomized patients per treatment arm (in 1:1 allocation ratio to vildagliptin + metformin and metformin monotherapy) is planned.

The sample size calculation assumed that all randomized patients are to be followed up for 5 years unless patients dropped out from the study for various reasons (lack of efficacy, AEs, abnormal labs, lost to follow-up etc.). Including the updated information of the yearly dropout rate being approximately 4% (based on observed discontinuation rate for this study at the time of completion of the trial).

The existing vildagliptin study data suggest that approximately 10% of vildagliptin patients will have an HbA1c >7.0% after the first 3 months of the study (initial response phase), since those patients who are randomized with an HbA1c measurement above the failure threshold (7.0%) may never have an HbA1c measurement below the required threshold during the study and will therefore be counted as failures during the first 13 weeks. A similar proportion is assumed for the comparator arm. Hence it is expected that the difference in failure rate is likely to be small early in the study, but will diverge as the study progresses. The power calculations have been adjusted to take this assumption into account using statistical simulations.

The simulations showed that assuming an annual initial treatment failure rate of 7.1% in the metformin monotherapy arm (estimated based on ADOPT data), incorporating a 10% initial failure rate after 13 weeks in each treatment arm (due to some patients with baseline HbA1c $\geq 7.0\%$), 1000 patients per treatment arm would be sufficient to detect a hazard-ratio of 0.75 between vildagliptin + metformin and metformin alone (corresponding to a risk reduction rate of 25% in vildagliptin + metformin group versus metformin alone) with approximate 75% power and a 1-sided significance level of 0.025 (corresponding to a 2-sided test at 0.05).

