3	06May2019	
Section 1.4 Changed duration derivation from weeks to Months.
 
Section 1.6 Added the list of AEs of special interest
 
Section 2.1.2 Added information of efficacy parameters to be considered for deviation code N02 and N03.
 
Section 2.1.5 Removed definition of baseline HbA1c and FPG as it was redundant. Baseline is already defined in section 1.1
 
Section 2.1.5 redefined age classification based on tertiles
 
Section 2.1.6 redefined exposure categories in months instead of weeks.
 
Section 2.2.1 Added table mentioning grouping for geographical regions
 
Section 2.2.2 Removed loss of glycemc control as primary endpoint; provided additional detail to used confirmation visit for time to initial treatment failure; Since we have only one primary endpoint, removed multiple testing methods section
 
Section 2.2.2.4 Added time to first treatment failure as supportive analysis; modified age categories for subgroup analysis; added smoking status, region and beta cell functional and insulin resistance as subgroups of interest; removed ethnicity
 
Section 2.2.3 Added rate of glycemc control over time as secondary endpoint; [REDACTED]

[figure not shown]
Version	Date	
		
analyzed and it is outside the scope of the SAP
 
Section 2.2.3.3 Added the analysis of rate of glycemic control over time in this section
 
Section 2.3.5 Added clarification on using chi square test to compare events only if we have sufficient observed events.
 
Section 2.7 Updated power calculations based on single primary endpoint and updated yearly dropout rate.

Addendum 1	17Dec2019	
Section 2.2.2.4 Time to second treatment failure endpoint is added as a post-hoc analysis
 
Section 2.2.2.4 Subgroup analysis for the primary endpoint is added as a post-hoc analysis.
 
Section 2.7 Updated sample size section based on the protocol amendment 4

Table of contents

Clinical Development	1
List of abbreviations	6
1 Definitions and general strategy	7
1.1 Baseline definitions	7
1.2 Last On-Treatment Observation (Endpoint Observation)	7
1.3 General data handling strategy	8
1.3.1 Output data precision	8
1.3.2 Efficacy Assessment Window / Week X Measurement	8
1.3.3 Laboratory visit windows.....	9
1.3.4 Multiple laboratory measurements within same day	10
1.4 Duration of exposure to study medication.....	10
1.5 Treatment-Emergent Adverse Events	10

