2.8 Changes in the conduct of the study or planned analyses

The following change in the analysis is proposed in protocol amendment 3 (4th Oct 2016) which defers with the analysis proposed in this document. These proposed changes have come about through development of the RAP modules and discussions around the analyses.

- Treatment start date to be defined as the earliest vildagliptin/placebo date, as recorded on the DAR page of the eCRF (i.e. do not use visit 3 date). Consistently use this definition for day 1 and durations related to day 1.
- '+1' should be included in duration of exposure calculation when last study drug date is available.
- '+1' should not be included in duration of exposure calculation when last study drug date is missing/incomplete.
- Further detail added to better define the analysis sets.
- Geographic region to be included as a classification variable in the analysis of time to initial treatment failure (and all similar analyses).
- In the analysis of rate of loss in glycaemic control over time, time will be included as a fixed effect and as a random effect.
- In the analysis of time to insulin initiation, patients who complete the study in Period 1 or Period 2 will be censored at their last study visit.
- OGIS formula revised as per 23135 study.
- Due to the large number of patients (patients will be recruited until we have the required amount) and the robustness of analyses methods we can assume we will have sufficient patients data for the beta-cell function, insulin sensitivity, AUC of ISR/G and OGIS analyses.

█ [REDACTED]

█ [REDACTED]

- The definition of initial treatment failure is revised to be the date of the second of the two consecutive measurement of HbA1c value $\geq 7\%$. The rationale of this change is that this will be consistent with the Period 1 end date definition. The decision of this definition update is documented in the RAP II meeting minutes in RAP Module 1.
- Main analysis approach includes only one primary endpoint in this SAP. As the probability and risk of time to initial loss of glycaemic control as primary efficacy variable is presented as a hazard ratio and failure rate over time, the statistical approach and power calculations (including the impact of the known retention) was updated accordingly while moving the assessment of the rate of loss of glycaemic control by an annualised slope of mean HbA1c over time from week 26 to the end of period 1 to be a key secondary analysis instead.

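### SAP Addendum 1 section 2.7 states 75% power at 11% yearly dropout; the protocol gives 66% for the same inputs, and the 75% belongs to about 4% dropout

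*SAP*

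**What the plan says.** Three texts describe the power of the primary time-to-failure comparison.

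- **Protocol section 9.6 (under Amendment 4).** 11% yearly dropout, estimated from ADOPT, "with approximate 66% power and a 1-sided significance level of 0.025".
- **SAP V3.0 section 2.7.** The dropout assumption is replaced by a "yearly dropout rate being approximately 4" percent, "based on observed discontinuation rate for this study at the time of completion of the trial". The stated power is about 75%.
- **SAP Addendum 1 section 2.7.** The text returns to the protocol's assumption, "and that the yearly dropout rate is 11% (estimate based on ADOPT data", and concludes "with approximate 75% power and a 1-sided significance level of 0.025".

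The document history of Addendum 1 explains the change to section 2.7: "Updated sample size section based on the protocol amendment 4". Section 2.8 of the addendum still carries the V3.0 statement that the "power calculations (including the impact of the known retention) was updated accordingly".

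**The concern.** With everything else fixed, more dropout means fewer observed failures and less power. Addendum 1 nevertheless reports the same power at 11% dropout as V3.0 reported at 4%, and a higher power than the protocol reports for identical inputs. It looks as though the update carried over the dropout rate from Amendment 4 but not the power that goes with it.

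What is at stake is the stated sensitivity of the only primary test. At 66% power the type II error under the design alternative is 34%; at 75% it is 25%. A reader of the latest SAP would take the more favourable figure as resting on the planning assumption. Section 2.8 meanwhile suggests that it rests on achieved retention.

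**Working it through.** **1. The texts side by side**

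| Input | Protocol 9.6 | SAP V3.0, 2.7 | SAP Addendum 1, 2.7 |
|---|---|---|---|
| Patients per arm | 1000 | 1000 | 1000 |
| Follow-up | 5 years | 5 years | 5 years |
| Annual failure, metformin | 7.1% | 7.1% | 7.1% |
| Initial failures at week 13, each arm | 10% | 10% | 10% |
| Hazard ratio | 0.75 | 0.75 | 0.75 |
| One-sided alpha | 0.025 | 0.025 | 0.025 |
| Yearly dropout | 11% | about 4% | 11% |
| Stated power | 66% | 75% | 75% |

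The first and third columns differ only in the last row, by 75 − 66 = 9 points. The second and third differ only in dropout, yet state the same power.

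**2. Reproducing the stated figures by simulation**

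Model: one-sided log-rank test at 0.025 (an unadjusted stand-in for the Cox test); 10% of each arm fail at week 13 regardless of treatment; the rest fail exponentially, at 7.1% per year on metformin and hazard ratio 0.75 on the combination; exponential dropout; 5 years. With the rates read as annual probabilities, continuous event times and 10,000 runs:

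- 11% dropout: power 0.646, about 575 events. This is within 2 points of the protocol's 66%.
- 4% dropout: power 0.730, about 648 events. This is within 2 points of V3.0's 75%.

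The simulated gap is 73.0 − 64.6 = 8.4 points, close to the documents' 9. The Monte Carlo standard error is about √(0.646 × 0.354 / 10,000) = 0.5 points.

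**3. Cross-check by formula**

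Let λ be the failure hazard in an arm and μ the dropout hazard. Metformin: λ = −ln(1 − 0.071) = 0.0736. Combination: 0.75 × 0.0736 = 0.0552.

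- Late events per arm: 900 × λ/(λ + μ) × (1 − exp(−5(λ + μ))). D is the sum over both arms.
- Initial failures in both arms: I = 200 × exp(−0.25μ).
- Late events carry the treatment difference, while all events add to the variance: z = 0.25 × D × |ln 0.75| / √(0.25 × (D + I)), and power = Φ(z − 1.96).

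*11% dropout:* μ = −ln(0.89) = 0.1165. D = 213.9 + 166.8 = 380.7 and I = 194.3. z = 27.38/11.99 = 2.284, so power = Φ(0.324) = 0.627.

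*4% dropout:* μ = −ln(0.96) = 0.0408. D = 252.4 + 197.4 = 449.7 (rounded) and I = 198.0. z = 32.34/12.72 = 2.542, so power = Φ(0.582) = 0.720.

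**4. Can any reading give 75% at 11% dropout?**

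The simulation was varied: rates as hazards or as annual probabilities, continuous or 13-weekly event times, later failures counted from randomisation or from week 13, dropout from day 0 or from week 13, and a random or fixed number of initial failures. Across these variants power was 58–65% at 11% dropout and 67–74% at 4%.

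Higher values at 11% appear only when the dilution from initial failures is left out. Simulation with no initial failures gives 0.83–0.84, and a plain Schoenfeld formula on late events alone gives 0.77–0.80. Section 2.7 says that the initial failures were incorporated. The same shortcuts at 4% give 0.89–0.90 and 0.84–0.86, so they cannot yield both 66% at 11% and 75% at 4%.

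**The case against.** The strongest reply concerns scope and weight; the mismatch itself is not disputed.

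- **The comparison with V3.0 is provenance.** That text is superseded, so differing from it is not an error. This stands. The live conflict is between protocol 9.6 and Addendum 1 section 2.7, and V3.0 only shows where the 75% came from.
- **Section 2.8 is a list of changes relative to protocol amendment 3, carried over unchanged from V3.0.** This is partly right, and the finding does not depend on it. It is still current text in the addendum that explains this SAP's power figure, and it does not fit an 11% planning rate, so it should be aligned when section 2.7 is edited.
- **The basis is stated: 11%, from ADOPT, following Amendment 4.** This is also right, and it favours correcting the power to 66% over going back to 4% dropout.
- **The simulations do not hit 66% or 75% exactly.** This is true. The plan's simulation code, dropout distribution and timing of initial failures are not given, and with 13-weekly event times the results are 0.629 and 0.724. The simulations support the direction and approximate size of the dropout effect; they cannot certify 66% to the point.
- **Nothing in the trial changes.** This is true. V3.0 already cites retention at trial completion, and the addendum adds analyses labelled post hoc. That limits the consequence, but the figure is still wrong as written.

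**Conclusion.** The concern holds. Addendum 1 section 2.7 attaches to 11% dropout a power that the documents support only for about 4%. The overstatement is 9 points against the protocol's own figure. This conclusion needs only the three texts. The recalculation supports it, assuming exponential failure and dropout and the stated 10% initial failures unaffected by treatment. It is a mismatch left by an incomplete update and affects only the reported power. It should be corrected because the figure describes the only primary hypothesis and errs in the favourable direction.

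**What to change.** Choose one consistent pair in Addendum 1 section 2.7:

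- **(a)** 11% yearly dropout with about 66% power, matching protocol 9.6. The document history indicates that this was the intent, so it is the simpler correction.
- **(b)** About 4% yearly dropout with about 75% power, labelled as based on the retention observed in the trial, with a sentence explaining why it differs from protocol 9.6.

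Then make the retention statement in section 2.8 agree. Under (a), it should say that the retention-based calculation belonged to V3.0.

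The cost is a text edit in two sections, with no new simulation and no change to the trial or its analysis. Option (a) means reporting a less favourable power; option (b) means carrying a documented departure from the protocol.
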